**PRESENTATIONS OF ENDPOINT SUMMARIES WILL ALSO BE PERFORMED BY SITE. NO INFERENCES WITHIN SITE WILL BE PROVIDED.**

~~P-values will be provided to test for non-zero changes from baseline in all measures.~~ Due to the exploratory nature of the study no correction of **FOR** multiple testing will be performed.

**THE ASSUMPTION OF NORMALITY AND HOMOGENEITY OF VARIANCE IN THE ANCOVA MODEL WILL BE INVESTIGATED. VIOLATION OF THESE ASSUMPTIONS MAY BE OVERCOME USING SUITABLE TRANSFORMATION OR PERFORMING A NON-PARAMETRIC TEST (E.G., THE WILCOXON SIGNED-RANK TEST).**

 GlaxoSmithKline	Document Name	Clinical Protocol 204930		
	Type	Version	Document Identifier	Effective Date
	eldo_clinical_doc	6.0; Most-Recent; Effective; CURRENT	090032d580c189ed	12-Sep-2016 05:12:55
	Reason For Issue	Auto Issue		

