## 4 Sample Size Determination

The sample size is based on DHEQ total Score, restrictions, adaptation, social impact, emotional impact and identity, from a previous study [GSKCH Study RH01897].

A sample size of 60 subjects will have at least 90% power to detect significant changes to week 24 for each of the DHEQ variables, with a significance level (alpha) of 0.05 using a two-sided one-sample t-test. No adjustments for multiple testing have been used. Approximately 75 eligible subjects will be allocated the study toothpaste in order to ensure that approximately 60 subjects complete the study. Sixty subjects

 GlaxoSmithKline	Document Name	SAP 204930.doc		
	Type	Version	Document Identifier	Effective Date
	eldo_clinical_doc	1.0; CURRENT; Most-Recent; Effective	090032d580cb2f1e	10-Nov-2016 09:05:48
	Reason For Issue	Auto Issue		

will provide reasonable precision on estimates of DHEQ response and clinical DH assessments.

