# 8 Efficacy Analysis

## 8.1 Primary Analysis

The null hypothesis for the primary analysis will be:

$H_0$ = There is no difference from baseline in DHEQ endpoints over time.

The alternative hypothesis will be:

$H_1$ = There is statistically significance difference from baseline in DHEQ endpoints over time.

The following DHEQ endpoints will be analysed:

- Section 1, questions 7, 8 and 9 as separate questions
- Total Score (34 item total from Section 2 questions 1 to 34)
- Domains:
  1. Restrictions (4 item total from Section 2 questions 1 to 4)
  2. Adaptation (12 item total from Section 2 questions 5 to 16)
  3. Social Impact (5 item total from Section 2 questions 17 to 21)
  4. Emotional Impact (8 item total from Section 2 questions 22 to 29)
  5. Identity (5 item total from Section 2 questions 30 to 34)
- Global Oral Health Rating (response to Section 2 question 35)
- Effect on Life Overall (4 item total from Section 2 questions 36 to 39)

 GlaxoSmithKline	Document Name	SAP 204930.doc		
	Type	Version	Document Identifier	Effective Date
	eldo_clinical_doc	1.0; CURRENT; Most-Recent; Effective	090032d580cb2f1e	10-Nov-2016 09:05:48
	Reason For Issue	Auto Issue		

Above DHEQ endpoints will be analysed using mixed effect ANOVA with Visit and site as fixed effect, subject as random effect. Adjusted Means will be computed for each visit. Using this model, the post baseline visit will be compared to the baseline visit and difference of their effect will be computed along with P-values and 95% confidence interval.

The visit by site interaction will be investigated by including the visit by site interaction term. If the visit by site interaction term is not significant at the 10% level of significance then this term will be removed from the model.

If the visit site interaction term is significant at 10% level of significance then the interaction will be included in the model and all model estimates (Adjusted Means, 95% CIs and P-values) for within and between visits will be reported separately for each site and based on results from visit by site interaction.

Each of the DHEQ endpoints will be summarised by time point (Baseline, Week 4, 8, 12, 16, 20 and 24).

Standard summary measures, 95% CIs and p- values will be presented. A plot of means of raw scores over time (mean  $\pm$  standard errors) will also be presented for all measures.

Due to the exploratory nature of the study no correction of multiple testing will be performed.

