Summary statistics (N, Percentage) will be provided for section 1 (Q1-Q6) and section 2 (Q1 - Q39) of DHEQ questionnaire.

The assumption of normality and homogeneity of variance in the ANOVA model will be investigated. Violation of these assumptions may be overcome using suitable transformation or performing a non-parametric test (e.g., the Wilcoxon signed-rank test).

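### After looking at diagnostics, the plan lets a Wilcoxon signed-rank test stand in for the mixed model; the test discards incomplete pairs and overstates improvement if non-improvers leave early

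*SAP*

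**What the plan says.** SAP 8.1 sets the primary analysis: "Above DHEQ endpoints will be analysed using mixed effect ANOVA with Visit and site as fixed effect, subject as random effect". Each post-baseline visit is compared with baseline, a visit-by-site interaction is tested at the 10% level, and results are given by site if it is significant. Then comes the check: "The assumption of normality and homogeneity of variance in the ANOVA model will be investigated". The remedy follows: "Violation of these assumptions may be overcome using suitable transformation or performing a non-parametric test", with the Wilcoxon signed-rank test as the example. SAP 8.2 repeats this for Schiff and LMS. Protocol 9.3.2 and 9.3.3 carry the same sentence ("VIOLATION OF THESE ASSUMPTIONS MAY BE OVERCOME USING SUITABLE TRANSFORMATION OR PERFORMING A NON-PARAMETRIC TEST"), although there the model is called ANCOVA.

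Neither document names a diagnostic, a threshold, a decision-maker or an order between the two remedies. Neither says whether the remedy replaces the mixed model or only supports it.

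Four other provisions matter:
- Protocol 9.2.6 rules out imputation.
- SAP 5.1 admits a subject to ITT with one post-baseline assessment, so some ITT subjects will have no Week 24 value.
- SAP 4 plans for attrition: "Approximately 75 eligible subjects will be allocated the study toothpaste in order to ensure that approximately 60 subjects complete the study".
- The Protocol Amendment Page records that Amendment 3 moved from a paired t-test to the mixed model to account for site.

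**The concern.** Residual diagnostics need a fitted model, so the results are visible when the choice of method is made. The study has one arm, and Protocol 5.8.2 says that neither staff nor sponsor is blinded. The choice can differ across the 11 DHEQ measures listed in SAP Appendix 3. Diagnostics may well look poor, since several measures are single 1-to-10 ratings or a six-category rating.

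The named fallback changes more than the distributional assumption. The mixed model uses the earlier visits of a subject who leaves. The signed-rank test of baseline against Week 24 drops that subject. The missing-data assumption therefore moves from missing at random, given a correct covariance, to completers being representative. It also returns to a paired test, which Amendment 3 had replaced, and cannot deliver the planned visit-by-site analysis. If poor responders tend to leave, the reported improvement is too large and is declared too often.

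**Working it through.** **Inputs from the documents.** 75 allocated and 60 completing; alpha 0.05 two-sided; at least 90% power with 60 subjects (SAP 4). Baseline plus six post-baseline visits. No imputation.

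**The plan's own figure.** SAP 4 states: "A sample size of 60 subjects will have at least 90% power to detect significant changes to week 24". It gives no effect size or SD, only a previous study, so the 90% can be neither confirmed nor refuted. Solving the noncentral-t power equation for n = 60 gives an implied standardised change of 0.425. The normal approximation is (1.960 + 1.282)/√60 = 0.418. With an assumed within-subject correlation of 0.6, the SD of change is √(2 × 0.4) = 0.894 baseline SD, so the implied change is 0.425 × 0.894 = 0.38 baseline SD.

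**Lost pairs.** 1 - 60/75 = 0.20, so up to 15 of 75 subjects have no Week 24 pair. Schiff and LMS may lose more, because Protocol 4.4 omits clinical efficacy measures at some attended visits.

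**Outputs.** The shells for Tables 9.3.1.3 and 9.3.2.2 ask for adjusted means, differences, CIs and p-values, all footnoted to the mixed model. A signed-rank test supplies a p-value and, at most, a Hodges-Lehmann interval.

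**Simulation 1: correlation 0.6.** 75 subjects, 7 visits, 2 sites, 600 runs per row, about 17% lost by Week 24. A REML random-intercept model (visit and site, all data) is set against Wilcoxon on baseline/Week 24 pairs. The outcome-dependent dropout rule is logit(hazard) = -4.0 + 1.5 × change from baseline, measured relative to the true trend. Estimates are in baseline SD; negative means improvement. The last two columns give the rate of falsely declaring improvement (nominal 2.5%).

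| Dropout, true change 0 | Mixed estimate | Paired estimate | Mixed | Wilcoxon |
|---|---|---|---|---|
| Completely random | -0.01 | -0.01 | 2.7% | 2.7% |
| After worse observed change | 0.00 | -0.10 | 3.2% | 12.8% |
| Same, plus random slopes | -0.03 | -0.13 | 6.7% | 15.5% |
| Depends on the unseen value | -0.04 | -0.11 | 6.5% | 16.8% |
| After worse observed change, skewed errors | +0.03 | -0.05 | 2.0% | 7.3% |

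Monte Carlo error is about 0.005 on estimates and up to about 1.5 percentage points on rates. With a true change of -0.38 and dropout after worse observed change, the mixed model gave -0.39 and the paired estimate -0.48. That overstates the change by 0.10/0.38, about 26%.

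**Simulation 2: is the mixed model itself safe?** Same size, no true change, about 20% lack-of-improvement dropout, two-sided 5% tests, over a wider range of settings:
- The paired estimate was biased by -0.08 to -0.21 SD, and Wilcoxon rejected in 10-29%.
- With correlation decaying between visits (AR(1)), the random-intercept model with model-based standard errors rejected in about 16-23%.
- Empirical standard errors from the same model brought this to about 4-8%. A bias of -0.06 to -0.09 SD remained under informative dropout.

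Under AR(1) correlation of 0.8-0.9 per visit and uninformative dropout, a separate run gave 14-19% for the model-based test and 5-7% for Wilcoxon.

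**Non-normality and unequal variance.** With strongly skewed data (chi-square, 3 df) and uninformative dropout, the mixed model rejected in 5.8%, with 94.5% coverage. With visit SDs falling from 1 to 0.7, it rejected in 7.6% against 4.8% for Wilcoxon. With SDs rising to 1.4, the figures were 5.4% and 4.0%.

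**The case against.** The strongest case is that the mixed model looks better only because it was simulated under its own covariance. This stands in part. With decaying correlation and uninformative dropout, the model-based test is worse than Wilcoxon. A reader might infer that the planned model is unbiased and holds its 5% level as written. It does so only if the exchangeable correlation is right.

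Other readings go too far:
- **Unequal variance.** A reader might think Wilcoxon fails when variances differ between visits. A signed-rank test uses only that visit's own differences and needs no equal variance across visits. The pooled random-intercept model does.
- **Transformation.** It does not drop pairs or site. It keeps the model and the partial data, and changes only the scale, so that the result is no longer in DHEQ points.
- **Site.** An additive site effect cancels within subject. What is lost is the interaction analysis; by-site summaries and figures are planned anyway.
- **Certain replacement.** The text says the remedy may be used. The shells have no Wilcoxon row, and raw means and changes are tabulated regardless. Even so, nothing keeps the mixed model as the reported result.

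The stakes are also limited. The study is described as exploratory, has no formal success criteria and applies no multiplicity correction. The documents do not say why subjects would leave, and random dropout gives no bias. These points limit the severity. They do not justify a fallback that discards up to a fifth of subjects at Week 24.

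**Conclusion.** The concern holds in this form: the plan permits a post-hoc, endpoint-by-endpoint move to a signed-rank test that discards incomplete pairs, gives up the visit-by-site analysis and cannot fill the model-based shells. The loss of pairs follows from the plan's own 75 and 60. The bias of about -0.08 to -0.21 SD and the 10-29% rejection rest on an assumed tendency of non-improvers to leave, and on assumed correlations. Under completely random dropout the bias is zero, and it would reverse if improvers left.

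The documents do not support the stronger conclusion that the mixed model as specified is the safe alternative. It becomes the better choice once its standard errors no longer depend on the random-intercept covariance. Even then a smaller bias can remain under informative dropout. The change should be made, but it does not touch the design or data collection.

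**What to change.** In SAP 8.1 and 8.2, replace the sentence on violated assumptions with:

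> The mixed model on the original scale is the reported analysis whatever the diagnostics show, always with small-sample-corrected empirical (sandwich) standard errors or a subject-level bootstrap CI. Any Wilcoxon signed-rank or transformed-scale result is a labelled sensitivity analysis.

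The word always matters. Making robust errors conditional on the residuals would keep an undefined trigger and would miss a misspecified correlation. Choose one of the two interval methods before database lock. Align Protocol 9.3.2 and 9.3.3.

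The cost is wording and one procedure option, with no change to conduct. The downside is small: at 60-75 subjects the empirical standard errors need the small-sample correction. They also correct the error rate and not the estimate, so the report should say that some bias may remain if dropout is related to response.

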## 8.2 Exploratory Analyses

The following exploratory analyses will be conducted.

At each time point the mean Schiff Sensitivity Score (for the two test teeth and all qualifying teeth) and mean LMS scores [each of 4 scales (description, tolerability, description, intensity)] as well as the change from baseline will be calculated.

 GlaxoSmithKline	Document Name	SAP 204930.doc		
	Type	Version	Document Identifier	Effective Date
	eldo_clinical_doc	1.0; CURRENT; Most-Recent; Effective	090032d580cb2f1e	10-Nov-2016 09:05:48
	Reason For Issue	Auto Issue		

The above each endpoint will be analysed using mixed effect ANOVA with visit and site as fixed effect, subject as random effect. Adjusted Means will be computed for each visit. Using this model, the post baseline visit will be compared to the baseline visit and difference of their effect will be computed along with P-values and 95% confidence interval.

The visit by site interaction will be investigated by including the visit by site interaction term. If the visit by site interaction term is not significant at the 10% level of significance then this term will be removed from the model.

If the visit site interaction term is significant at 10% level of significance then the interaction will be included in the model and all model estimates (Adjusted Means, 95% CIs and P-values) for within and between visits will be reported separately for each site and based on results from visit by site interaction.

Standard summary measures, 95% CIs and p-values will be presented. A plot of means of raw scores over time (mean  $\pm$  standard errors) will also be presented for all measures.

The assumption of normality and homogeneity of variance in the ANOVA model will be investigated. Violation of these assumptions may be overcome using suitable transformation or performing a non-parametric test (e.g., the Wilcoxon signed-rank test).

The percentage of teeth that are sensitive (Schiff sensitivity score  $>0$  of all qualifying teeth from screening (termed 'the qualifying teeth') will be summarised for each timepoint and also plotted over time.

## 9 Safety Analysis

The safety profile of the study dentifrice will be assessed with respect to adverse events (AEs). Oral soft tissue (OST) abnormalities are included as AEs if they appear or worsen after the initial assessment.

All safety data will be reported for the Safety population as per actual treatment received. All subjects screened will be included in the list of AEs.

All AEs will be reviewed by the Clinical Research Director or Designee prior to database freeze and will be coded using the Medical Dictionary for Regulatory

 GlaxoSmithKline	Document Name	SAP 204930.doc		
	Type	Version	Document Identifier	Effective Date
	eldo_clinical_doc	1.0; CURRENT; Most-Recent; Effective	090032d580cb2f1e	10-Nov-2016 09:05:48
	Reason For Issue	Auto Issue		

Activities (MedDRA). During this review stage, AEs will be further categorized as oral or non-oral.

AEs will be regarded as treatment emergent if they occur on or after the start date and time of the first treatment application. All other AEs prior to this will be considered non-treatment emergent.

The following summary tables and listings will be presented by treatment group.

- Table of treatment emergent AEs by Oral/Non-Oral and Preferred Term
- Table of treatment emergent AEs by SOC and Preferred Term
- Table of Treatment emergent treatment related AEs by Oral/Non-Oral and Preferred Term
- Listing of all AEs (including Non-treatment emergent from All Subjects).
- Listing of serious AEs. (if there are none a null listing will be produced, if there are >5 treatment emergent SAEs a table will be produced by SOC and PT)
- Listing of incidents (if there are none a null listing will be produced)
- Table of Non Serious treatment emergent AEs by SOC and Preferred Term. (only produced if there are > 5 SAEs)

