## 7. SAFETY ASSESSMENTS

### 7.1. Definitions of an Adverse Event and Serious Adverse Event

#### 7.1.1. Adverse Events

The investigator or site staff will be responsible for detecting, documenting and reporting events that meet the definition of an AE or SAE.

Adverse Event Definition:
 
 
• An AE is any untoward medical occurrence in a patient or clinical investigation subject, temporally associated with the use of an investigational or washout product, whether or not considered related to the investigational or washout product.
 
• NOTE: An AE can therefore be any unfavorable and unintended sign (including an abnormal laboratory finding), symptom, or disease (new or exacerbated) temporally associated with the use of an investigational or washout product.
 

--

Events meeting AE definition include:
 
 
• Any abnormal laboratory test results (if applicable) or other safety assessments, including those that worsen from baseline, and felt to be clinically significant in the medical and scientific judgment of the investigator.
 
• Exacerbation of a chronic or intermittent pre-existing condition including either an increase in frequency and/or intensity of the condition.
 
• New condition(s) detected or diagnosed after study product administration
 

--

 GlaxoSmithKline	Document Name	Clinical Protocol 204930		
	Type	Version	Document Identifier	Effective Date
	eldo_clinical_doc	6.0; Most-Recent; Effective; CURRENT	090032d580c189ed	12-Sep-2016 05:12:55
	Reason For Issue	Auto Issue		

- even though it may have been present prior to the start of the study.
- Signs, symptoms, or the clinical sequelae of a suspected interaction.
  - Signs, symptoms, or the clinical sequelae of a suspected overdose of either study product or a concomitant medication (overdose per se will not be reported as an AE/SAE).

- Events NOT meeting definition of an AE include:**
- Any clinically significant abnormal laboratory findings (if applicable) or other abnormal safety assessments which are associated with the underlying disease, unless judged by the investigator to be more severe than expected for the subject's condition.
  - The disease/disorder/ condition being studied or expected progression, signs, or symptoms of the disease/disorder being studied, unless more severe than expected for the subject's condition..

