## 7.5. Follow-up of Adverse Events and Serious Adverse Events

### Follow-up of AEs and SAEs:

- After the initial report, the investigator is required to proactively follow up with each subject and provide further information on the subject's condition.
- All AEs/SAEs will be followed until resolution, until the condition stabilizes, until the event is otherwise explained, or until the subject is lost to follow-up.

 GlaxoSmithKline	Document Name	Clinical Protocol 204930		
	Type	Version	Document Identifier	Effective Date
	eldo_clinical_doc	6.0; Most-Recent; Effective; CURRENT	090032d580c189ed	12-Sep-2016 05:12:55
	Reason For Issue	Auto Issue		

- The investigator is obligated to perform or arrange for the conduct of supplemental measurements and/or evaluations as may be indicated or as requested by GSK to elucidate as fully as possible the nature and/or causality of the AE or SAE.
- Investigators are not obliged to actively seek AEs or SAEs in former subjects. However, if the investigator learns of any SAE, including the death, at any time after a subject has been discharged from the study, and considers the event reasonably related to the investigational product or study participation, the investigator will promptly notify GSKCH.
- The investigator will submit any updated SAE data to GSK within the designated reporting time frames.

Regulatory and ethics reporting requirements for SAEs:

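### The SAP's treatment-emergent rule has no worsening clause, so an acclimatisation-phase AE that worsens on the study toothpaste may miss the AE tables, depending on how it is recorded

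*SAP*

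**What the plan says.** SAP section 9 (Safety Analysis) gives a two-part rule: "AEs will be regarded as treatment emergent if they occur on or after the start date and time of the first treatment application", and then "All other AEs prior to this will be considered non-treatment emergent". Neither sentence mentions an AE already present that gets worse.

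The same section does mention worsening when it says which oral soft tissue findings count as AEs: "Oral soft tissue (OST) abnormalities are included as AEs if they appear or worsen after the initial assessment".

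Protocol 7.1.1 also treats worsening as a possible AE. Its examples include "Exacerbation of a chronic or intermittent pre-existing condition including either an increase in frequency and/or intensity of the condition", and abnormal safety assessments, "including those that worsen from baseline, and felt to be clinically significant in the medical and scientific judgment of the investigator". The note to its AE definition covers both new and exacerbated signs, symptoms or disease, and it names the washout product as well as the investigational one.

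Protocol 7.5 adds a follow-up duty: "All AEs/SAEs will be followed until resolution, until the condition stabilizes", or until the event is otherwise explained or the subject is lost to follow-up.

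**The concern.** A treatment-emergent definition normally has two arms: onset after first treatment, and worsening after first treatment of something already there. The SAP has only a timing rule. That matters here because every subject uses another toothpaste for 3 to 6 weeks under AE surveillance before starting the study product, so an AE can be open when treatment begins. Aggravation of an existing oral irritation after the switch is a plausible tolerability signal for a toothpaste.

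SAP section 9 assesses the product's safety profile through AEs, and the AE summary tables are restricted to treatment-emergent events. If an aggravated run-in AE keeps its run-in date, it is absent from the oral/non-oral table, the system organ class table and the treatment-related table. With one arm and about 75 treated subjects, treatment-related oral AEs may be few, and then one or two cases would be noticeable.

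**Working it through.** The documents give no AE rates and no figure on this point, so the check is a comparison of sections.

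**1. Can a run-in AE be open at Visit 2?** Yes. The visit descriptions (Protocol synopsis and 3.1, SAP section 3) and footnote 4 of the Schedule of Events start AE documentation after the supervised acclimatisation brushing at Visit 1. Acclimatisation lasts 3 to 6 weeks. Protocol 6.1.6 records as an AE an application-site abnormality that follows either the acclimatisation or the study toothpaste. Protocol 7.2 differs: it starts AE collection with the investigational product and sends earlier conditions to medical history.

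**2. What is the first treatment application?** SAP section 9 does not tie it to Visit 2. The acclimatisation brushing is an unlikely reading. AEs are documented only from that brushing onward, so the non-treatment-emergent class would be nearly empty, yet the SAP plans a listing that includes it. The study-toothpaste brushing at Visit 2 is the sensible reading, but it is left to inference.

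**3. How is worsening recorded?** Protocol 7.3 assigns each AE one intensity category. Protocol 7.5 has the event followed until it resolves or stabilises. Neither says what happens to the record when intensity rises. The exacerbation example in 7.1.1 is limited to chronic or intermittent pre-existing conditions, and an acute irritation that began during acclimatisation does not clearly fit. The note to the definition is wider, but it says what can be an AE, not whether a second record is opened. The SAP's oral soft tissue sentence has the same limit: a finding that first appears during run-in already qualifies, and nothing says that its later worsening opens another AE.

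**4. What does the rule do in each case?**

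| Recording of the worsening | Date used | Class under SAP 9 | Where it appears |
|---|---|---|---|
| New AE record | After Visit 2 brushing | Treatment emergent | AE tables and listings |
| Kept on the original record | During acclimatisation | Non-treatment emergent | Listings only |

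The tables affected are 9.4.1, 9.4.2 and 9.4.3, and the conditional 9.4.6. Tables 9.4.1 and 9.4.3 are also the two topline AE tables. The event would remain in the all-AE listing (9.4.5, also topline), in Listing 2.1 if it is an oral soft tissue abnormality, and in the serious AE listing (9.4.4) if serious.

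**5. Illustrative size.** Both rates are assumptions. Suppose 5% to 10% of the 75 planned subjects have an open AE at Visit 2:

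- 75 × 0.05 = 3.75 and 75 × 0.10 = 7.5 subjects.

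Suppose 10% to 30% of those worsen on the study toothpaste:

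- Low: 3.75 × 0.10 = 0.375, about 0.4 subjects.
- High: 7.5 × 0.30 = 2.25 subjects.

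That is about 0 to 2 subjects. Under these rates it is the most that could be affected, because it assumes that every worsening stays on the original record.

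**The case against.** The strongest reply is that the documents already provide a route into the tables. The SAP says AEs that *occur*, not AEs that *start*, on or after first application, and a worsening can be said to occur when it happens. The definition note in Protocol 7.1.1 covers exacerbated symptoms with no restriction to chronic conditions. Oral soft tissue is examined at every visit, and worsening there counts as an AE under the SAP. On the Protocol 7.2 collection start, a run-in irritation would be medical history and its worsening a new AE. CRF completion instructions, which are not among the documents, may settle the matter.

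Much of this stands. It shows that the intent is to treat worsening as an AE, and that exclusion is not automatic. A reader might infer that a worsened run-in AE is necessarily classed non-treatment emergent, left out of every safety table and visible only in the all-AE listing. The documents do not support that: the result depends on how the event is recorded, and oral soft tissue and serious events have listings of their own.

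The reply does not close the gap. Reading *occur* either way is defensible, so two programmers could classify the same case differently. No section directs that worsening be given its own record and date, and Protocol 7.2 conflicts with the visit schedule on when AE collection begins.

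**Conclusion.** The point holds conditionally and is minor. The treatment-emergent rule lacks a worsening arm, and no recording rule in either document makes up for it. If worsening of an acclimatisation-phase AE stays on its original record, an on-treatment aggravation is reported as non-treatment emergent and leaves all the treatment-emergent tables. If it is entered as a new AE, nothing is lost.

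This rests on two readings: that first treatment application means the study toothpaste at Visit 2, and that AEs are documented during acclimatisation as the visit schedule states. The number of subjects is probably very small. The 0 to 2 range reflects assumed rates only, and no share of the treatment-related oral AEs can be worked out. No efficacy analysis is touched.

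**What to change.** In SAP section 9, define an AE as treatment emergent if it starts, or increases in intensity or frequency, on or after the first application of the study toothpaste at Visit 2. This also pins down which application is meant.

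Add a CRF completion note: worsening of an AE still ongoing from acclimatisation is entered as a new AE record with its own onset date and intensity. Without the note the new definition may not be programmable, because Protocol 7.3 assigns only one intensity category to each AE. The original record keeps its run-in date and stays non-treatment emergent, so the worsening is counted once.

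At the same time, reconcile the AE collection start in Protocol 7.2 with the visit schedule, since the new definition depends on run-in AEs being captured.

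The cost is one SAP sentence, one CRF note and a data query on AEs ongoing at Visit 2. The treatment-emergent count may rise slightly.
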